## **Initial and final examination**

During the initial and final examinations, the several tasks to the patient will be performed. Firstly the anamnestic data will be collected, then the ankle dorsiflexion range of motion will be measured using the "weight-bearing lunge test" (cm). Thompson's test and resistance test will be

performed at the same time. The area of greatest pain will be localized by palpation. Then patient will also perform AT loading tests on both legs — single leg heel rise test and single leg hop test. The patient will perform as many heel rises/hops using only one leg as possible in 30 seconds or until first sign of pain in Achilles tendon area. This will be also measured in asymptomatic leg.

Secondly, the patient will be asked to complete a validated Victorian Institute of Sports Assessment - Achilles questionnaire, which assesses the subjectively perceived severity of the disease and partly its impact on the quality of normal daily or sports activities.

The patient's maximal pain will be assessed using a standardized numerical rating scale (NRS) of pain. The patient will be asked about the maximum pain that could be caused by various factors, at the initial examination, at the last application and during the final examination.

Lastly, the ultrasonographic examination of patient's AT in both legs will be performed. This examination is described in the following chapter.

Both, initial and final examinations in each patient will be performed by only one person (the investigator of the study) and the same person will prepare and perform each application of ESWT or sham-ESWT.

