### **Ultrasonographic examination**

USG examination will be performed with a Mindray DC-70 machine with a linear probe type L12-3E with a frequency of 12 Hz in the preset "MSK" mode. The whole area of AT will be monitored from the connection of soleus fibers to the insertion site on the calcaneus by longitudinal and transverse imaging.

The echotexture and continuity of the tendon, the echotexture of KFP, the presence of RC bursa, calcifications and osteophytes will be evaluated visually. At the same time, the possible degree of vascularization in or around the tendon will be evaluated using Doppler mode.

The values of anteroposterior tendon width, paratenon thickness, and CSA at the anteroposterior widest point will be collected using the measuring instruments included in USG machine.

USG findings will be consulted and evaluated in cooperation with an expert in USG diagnostics to increase their relevance and reduce the error rate.

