**Graphically represented study design:**

## **Data analysis**

In this study, the comparison of the results in groups A and B in the final examination compared with the baseline values will be evaluated.

Firstly, descriptive statistics (mean, median, standard deviation, minimum and maximum) of the initial and final values in both groups will be performed. Normal data distribution will be determined by the calculated Shapiro-Wilk p-value.

Then, a two-way ANOVA tests will be used to evaluate the statistical significance of effects comparison in both groups for most of the measured parameters (not including the tendon loading tests). Also the Tukey method will be performed to determine effects of each part of ANOVA testing.

In addition, paired t-tests or the Wilcoxon test will be performed for each group of each parameter. Thus, the statistical significance of the changes in the most of the parameters for each group will be calculated.

The number of repetitions in Achilles tendon loading tests (single leg heel rise / hop test) will only be analyzed by descriptive statistics to see the indicative change in results. There will also be collected a number of those patients who describe the pain during these tests.

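### No primary outcome or decisive test is named among six or so tested measures, so the A-versus-B question has no controlled error rate

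*Combined protocol and SAP*

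**What the plan says.** The Data analysis section gives the aim in general terms: "the comparison of the results in groups A and B in the final examination compared with the baseline values will be evaluated". For the test it says that "a two-way ANOVA tests will be used to evaluate the statistical significance of effects comparison in both groups for most of the measured parameters", leaving out only the heel-rise and hop tests. It continues: "Also the Tukey method will be performed to determine effects of each part of ANOVA testing". It then adds that "paired t-tests or the Wilcoxon test will be performed for each group of each parameter". On distributional checks it says: "Normal data distribution will be determined by the calculated Shapiro-Wilk p-value".

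The tested parameters are not listed there. Elsewhere the protocol collects these numerical measures outside the loading tests:

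- Initial and final examination: "the ankle dorsiflexion range of motion will be measured using the" weight-bearing lunge test, in cm.
- Same section: "the patient will be asked to complete a validated Victorian Institute of Sports Assessment - Achilles questionnaire".
- Same section: maximal pain on the NRS, asked at three time points.
- Ultrasonographic examination: "The values of anteroposterior tendon width, paratenon thickness, and CSA at the anteroposterior widest point will be collected".

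That makes six. A Doppler grade of vascularization is also recorded, and both legs are scanned; whether these results are tested is not stated.

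**The concern.** The aim identifies a contrast (A against B, final against baseline) but no parameter on which it will be judged. Nor does the plan say which ANOVA term answers it (group, time or group-by-time), whether time is a within-patient factor, what significance level applies, or how results are combined across parameters. Tukey's method limits error among the comparisons within one parameter's ANOVA. It does nothing across parameters and does not choose the deciding term. The within-group tests cannot answer a between-group question, yet their role relative to the ANOVA is left open.

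The plan does not tell anyone to select a favourable result, but nothing in it prevents this. If one measure, one term or an improvement in Group A alone is later put forward as evidence for ESWT, a reader cannot tell how often chance would have produced it.

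**Working it through.** The plan states no error rate, significance level or power, so there is no figure of its own to reproduce.

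**Inputs from the protocol.** At least 18 patients allocated 1:1 (Study design and description), so 18/2 = 9 per group; six numerical measures, as listed above.

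**Assumptions not in the documents.** Two-sided 0.05 per test; normal data; equal correlation r between measures; no treatment effect; no change over time unless stated. With two time points and time as a within-patient factor, the group-by-time test equals a two-sample t-test on change.

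**Step 1. Independent measures, closed form.**

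- At least one significant difference: 1 − 0.95^6 = 0.265 for six measures; 1 − 0.95^4 = 0.185 for four.
- At least one favouring ESWT: 1 − 0.975^6 = 0.141 for six; 1 − 0.975^4 = 0.096 for four.

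**Step 2. Correlated measures, simulation (60,000 trials per setting).**

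| Event | Measures | r = 0 | r = 0.5 | r = 0.9 |
|---|---|---|---|---|
| Any significant A–B difference | 6 | 0.265 | 0.212 | 0.111 |
| | 4 | 0.186 | 0.161 | 0.096 |
| Any favouring ESWT | 6 | 0.140 | 0.107 | 0.057 |
| | 4 | 0.097 | 0.081 | 0.049 |
| Any favouring ESWT, or Group A improved (paired t) | 6 | 0.225 | 0.170 | 0.092 |
| | 4 | 0.158 | 0.131 | 0.080 |

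For one fixed test the first row would be 0.05 and the rows favouring ESWT 0.025. A correlation of 0.9 is extreme for measures this different.

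**Step 3. Both groups improve equally.** The last rows of the table assume no change over time, which understates the hazard of within-group tests. Suppose both groups improve by 0.5 SD of the change and ESWT adds nothing. With 9 patients the paired t-test has power 0.263, so for one measure:

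- Group A significant: 0.263.
- A significant and B not: 0.263 × (1 − 0.263) = 0.194.

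For six independent measures, Group A is significant on at least one with probability 1 − (1 − 0.263)^6 = 0.84. At r = 0.5 simulation gives 0.65.

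**Step 4. If the ANOVA ignores pairing.** The plan's wording allows an ordinary two-way ANOVA with 36 − 4 = 32 error degrees of freedom. For six measures, the probability of at least one significant term is:

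| Term | r | Baseline–final correlation 0.3 | 0.5 | 0.7 |
|---|---|---|---|---|
| Group-by-time | 0 | 0.120 | 0.046 | 0.007 |
| | 0.5 | 0.099 | 0.039 | 0.006 |
| Group main effect | 0 | 0.409 | 0.497 | 0.574 |
| | 0.5 | 0.323 | 0.399 | 0.463 |

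The choice of term and error structure, which the plan leaves open, moves the rate from under 1% to over 50%.

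**Step 5. Why a single test must be fixed even for one measure.** With no effect, the chance that either an ANCOVA or a change-score test is significant is 0.078, 0.073 and 0.069 at baseline–final correlations of 0.3, 0.5 and 0.7, against 0.05 for either alone.

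**The case against.** The strongest reply is that the stated aim is change by group, so group-by-time is the natural term, and that the inflation depends on the reading. If pairing is ignored, the group-by-time rate across six measures is about 4–5% at a baseline–final correlation of 0.5 and under 1% at 0.7. This is correct. The 26% to 11% range belongs to the within-patient reading. The group main effect does not answer the aim, and part of its 32–57% comes from a wrong error term: even one measure gives about 8–13%. But a rate that falls below 5% only because the test ignores pairing is not error control; it makes the test of interest far too strict. The plan also still names no measure.

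Six is a count of numerical measures, not a firm ceiling. Testing the Doppler grade would raise it, and a narrower reading of the unlisted set would lower it.

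A small trial might be excused as exploratory, but the available text does not call it that and repeatedly refers to statistical significance. The statement of absence covers the text available for review, from the study design section to the data analysis section; the design figure is not shown.

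Finally, ANCOVA is a recommendation, not the only repair. Naming the group-by-time term with time as a within-patient factor would also close the gap.

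**Conclusion.** The concern holds. The available text fixes no primary outcome, deciding term, significance level or rule across parameters. Under the paired reading and the assumptions above, the chance of at least one false between-group difference is 11–26% for six measures and about 10–19% for four, against 5% for one fixed test. Counting only results that favour ESWT, it is 6–14% for six and 5–10% for four, against 2.5%. Claims based on Group A alone are worse if both groups improve for reasons unrelated to ESWT. The percentages rest on an assumed 0.05 level, normal data, equal correlations and 9 per group; the omission rests on none of these. This should be corrected before data are seen.

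**What to change.** Add to the Data analysis section, before any data are seen, text to this effect:

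> The primary outcome is the VISA-A total. The primary test is the A-versus-B difference at the final examination from an ANCOVA adjusting for baseline VISA-A, at two-sided 5%. The Shapiro-Wilk result does not change this test; a Wilcoxon rank-sum test on change is a sensitivity analysis. Lunge test, NRS pain at the final examination, tendon width, paratenon thickness and CSA are secondary, reported as between-group differences with 95% confidence intervals and not used to claim efficacy. Two-way ANOVA terms, Tukey comparisons and within-group tests are descriptive.

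The same text should give a role to NRS pain at the last application and to the Doppler grade (descriptive would do), and say whether the ultrasound finding used in allocation enters the model.

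VISA-A is the best supported choice: the protocol calls it validated, and it is completed by a patient who does not know the allocation. One person both examines the patients and applies every treatment, so that person is not blinded; a self-completed questionnaire is less exposed to this than measurements that person takes. The sponsor may justify another single outcome, or keep the ANOVA by naming group-by-time with time within patient, but only one test may be fixed.

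**Cost.** A short text change, with no new patients or data. A significant result on another measure could no longer be presented as proof that ESWT works.

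- **Power of the ANCOVA.** For a true difference of 1 SD of the final score with 9 per group, power is 52.5%, 60.0% and 76.5% at baseline–final correlations of 0.3, 0.5 and 0.7, against 39.3%, 51.4% and 72.9% for the within-patient group-by-time test. At a correlation of 0.9 the two are about equal (59.6% against 60.4% for 0.5 SD).
- **Non-normal data.** With exponential, lognormal or t(3) data the simulated ANCOVA type I error was 4.0–4.4%, so no Shapiro-Wilk switch is needed to hold 5%.
- **Secondary outcomes.** Formal adjustment is not asked for. At 0.05/5 = 0.01, t-test power for 1 SD of the change would fall from 51% to 25%.

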## **Study design and description**

This work is designed as a randomized, sham-controlled clinical trial in which we monitor the effects of low-energetic focused shock wave therapy (ESWT) on Achilles (AT) tendinopathy. We estimate that at least 18 patients will participate in it. They will be randomly divided into two groups in 1:1 ratio. Group A will receive ESWT according to selected parameters (see below). Group B will receive placebo in the means of sham-ESWT (see below).

Patients in both groups will have same program. The research within one patient will last in total of 8 weeks from the initial to the end examination. In the initial week the patient will be clinically examined by a physiotherapist, an ultrasonography (USG) examination will be performed and VISA-A questionnaire will be filled. At the end of this session, the patient will be randomly assigned to group A or B and receive first application (ESWT or sham-ESWT). For the next 4 weeks, once a week, the next applications will be performed. The interval between individual applications should be at least 5 days. Thus, a total of 5 applications of ESWT or sham-ESWT will be performed. The final examination will be performed at 3 weeks follow up after the last application and includes the same procedures as in the initial examination.

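### The A-versus-B difference in change is planned only as a significance test, with no confidence interval, so a non-significant result with about 9 patients per arm could not separate no effect from a large one

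*Combined protocol and SAP*

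**What the plan says.** All of this is in the Combined protocol and SAP.

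- **Question.** The Data analysis section states that "the comparison of the results in groups A and B in the final examination compared with the baseline values will be evaluated". That is a between-group difference in change.
- **Descriptives.** It plans "descriptive statistics (mean, median, standard deviation, minimum and maximum) of the initial and final values in both groups will be performed". Each visit is summarised separately; within-patient change is not summarised.
- **Between-group analysis.** "two-way ANOVA tests will be used to evaluate the statistical significance of effects comparison in both groups", for most parameters. The loading-test repetitions are excluded and stay descriptive.
- **Follow-up comparisons.** "Also the Tukey method will be performed to determine effects of each part of ANOVA testing". No contrast is named and no interval is requested.
- **Within-group analysis.** Paired t-tests or Wilcoxon tests are run in each group, and their stated product is again statistical significance.
- **Size.** Under Study design and description: "We estimate that at least 18 patients will participate in it" and "They will be randomly divided into two groups in 1:1 ratio". No significance level, power, target effect, SD or minimal important difference is given.

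**The concern.** The trial needs to show how much more group A changes than group B, and how precisely that is known. The planned outputs for this comparison are p-values and separate summaries of each visit. In a trial of this size a non-significant p-value is a likely result even when the true effect is moderate. On its own it does not tell the reader whether the data point to little effect or remain compatible with a large one. Within-group p-values will sit beside it, which makes it easy to compare significance in A with non-significance in B instead of looking at the difference itself. The interpretation of the main comparison, and how easily its change-score version can be reused, depend on reporting an estimate with an interval.

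**Working it through.** **Inputs.** From Study design and description: at least 18 patients, 1:1, hence 9 per arm at the minimum. Assumed, because the documents give no figure: two-sided 5% level, 95% interval, equal SDs in the two arms, complete data. Results are in units of the SD of change.

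**1. The plan's own figure.** The 18 cannot be reproduced, because no inputs are stated. Working backwards with 80% power, n per arm = 2 × (1.960 + 0.842)² / d² = 15.70 / d²:

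- d = 1.4 SD: 8.01, rounded up to 9; total 18
- d = 1.0 SD: total 32
- d = 0.8 SD: total 50
- d = 0.5 SD: total 126

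**2. Precision of the unadjusted difference in change.** Half-width = t(0.975, 2n − 2) × √(2/n) × SD of change. At 9 per arm this is 2.120 × √(2/9) = 2.120 × 0.4714 = 0.999, or about 1.0 SD.

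| Observed difference (SD) | 95% interval (SD) |
|---|---|
| 0 | −1.0 to 1.0 |
| 0.5 | −0.5 to 1.5 |
| 0.9 | −0.1 to 1.9 |

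All three rows are non-significant, yet they say very different things. Because 18 is a minimum, other sizes were checked: the half-width is 1.07 SD at 8 per arm, 0.94 at 10, 0.75 at 15 and 0.64 at 20.

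**3. How often the result would be non-significant.** Noncentral t with 16 df and noncentrality d × √(9/2) = 2.121 d gives power of 17% at d = 0.5, 36% at 0.8 and 51% at 1.0. Non-significance rates are therefore 83%, 64% and 49%. Power reaches 80% at d = 1.41. These rates come from the sample size. They show how often a reader would be left with a bare non-significant p-value.

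**4. What the planned descriptives allow.** The difference in mean change is (A final − A initial) − (B final − B initial), so it follows from the four planned means if the same patients are summarised at both visits. Its standard error does not follow from the visit SDs. With equal visit SDs, SD of change = SD × √(2(1 − r)), where r is the initial-to-final correlation, which is not planned as an output. In visit-SD units the half-width at 9 per arm is 1.41 at r = 0, 1.18 at 0.3, 1.00 at 0.5, 0.77 at 0.7 and 0.45 at 0.9, a threefold range.

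**5. What the test statistics allow.** A published paired t gives SD of change = |mean change| × √n / |t| for that group. If visit is treated as a repeated factor, the interaction F equals the squared t on change scores, and the standard error is |difference| / √F. The plan does not say whether the ANOVA is of that kind. In one simulated set of 18 patients, the t on change was 1.815 (squared, 3.29), while a two-way ANOVA ignoring the pairing gave an interaction F of 1.83. Recovering the standard error from that F would inflate it by √(3.29/1.83) = 1.34.

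**6. Tukey.** It compares pairs of means, such as A final with B final. The difference in change combines all four cell means and is not one of those pairs.

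**7. Gain from baseline adjustment.** With equal visit SDs, the leading term of the standard error is proportional to √(1 − r²) for ANCOVA and √(2(1 − r)) for change: 0.87 against 1.00 at r = 0.5, and 0.60 against 0.63 at r = 0.8. ANCOVA also spends one degree of freedom and loses a little to chance baseline imbalance, which these figures ignore.

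**The case against.** The strongest reply is that the plan gives more than it seems to. Much of it stands:

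- A reader might infer that the effect is never quantified. The documents do not support that, since the four planned means give the point estimate.
- A reader might infer that the result could not be pooled. That is also unsupported: final mean, SD and number per arm give a randomised comparison of final values, with a standard error, and no correlation is needed.
- The standard error for change may be recoverable from a paired t or an interaction F. This fails where Wilcoxon is used, where only a threshold p-value is reported, or where the ANOVA ignores the pairing.
- Tukey output often includes mean differences with intervals. The plan does not ask for them, and they would be for pairs of means.
- The power figures describe sample size, and an interval changes none of them.
- A reader might infer that the plan will treat a non-significant result as showing that ESWT is no better than sham. It contains no such rule. The plan is silent on interpretation.

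What survives is that the estimate answering the stated question is not planned as a result, and neither is its interval nor the SD of change.

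**Conclusion.** The point holds as a gap in planned estimation and reporting. The question is a between-group difference in change, and the analysis specified for it is described only by significance. The point estimate is derivable, but its interval can be rebuilt only by indirect routes that depend on unspecified choices. At the stated minimum the missing interval would be about ±1.0 SD of change, and still ±0.64 SD at 20 per arm, so a non-significant p-value alone cannot separate no effect from a large one. These figures assume a two-sided 5% level, an unadjusted t comparison of change, equal SDs and no dropout. The trial can run as designed; this is a change worth making before analysis.

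**What to change.** In the Data analysis section:

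- For each parameter now assigned to the two-way ANOVA, make the main between-group result an ANCOVA of the final value on group and baseline value. Report it as the A-minus-B difference with a 95% confidence interval, with the p-value secondary. The loading-test counts stay descriptive, as planned.
- Add mean and SD of within-patient change, by group, to the descriptives.
- State that a non-significant result will be interpreted from the interval and not taken as evidence of no effect.
- State the significance level and whether tests are two-sided.

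**Cost.** The ANCOVA is one additional simple model per parameter, because a group-by-visit ANOVA does not produce a baseline-adjusted estimate. It uses measurements already collected and needs no extra patients or visits. The report will show wide intervals, and the small sample size is not remedied.
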